6 STUDY OBJECTIVES

6.1 Main study objective

To document the non-inferiority of Lomatuell Pro® versus UrgoTul® on pain induced at first dressing removal in the management of acute wounds.

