7.2 Procedures and Assessments

7.2.1 Schedule of Assessments

All assessments of the investigation will be conducted as indicated in the following table which displays the frequency and timing of all measurements.

Table 1. Data collection schedule

	Inclusion Intermediate Ad		Additional	Final visit	Early Termination
	visit	visit	visits*	Final visit	visit**
Visit name (corresponding day)	V1 (D0)	V2 (D3±2)	Between V2 and V3	V3 (D21+2 or earlier, as soon as the wound is epithelialized completely)	ET
Oral consent of the patient to	X				
participate					
Inclusion/exclusion criteria	\boxtimes				
Randomization	X				
Demographics	X				
Medical history	X				
Wound/surrounding skin characteristics	×	×	×	X	X
Investigational product application	×	×	×		
Secondary dressing / fixation use	×	×	×		
Dressing removal (to follow the standardized removal procedure)		X	×	X	X
Intake of analgesics	X	×		×	×
Pain assessment (VAS) after application of investigational product	×				
Pain assessment (VAS) during removal		\boxtimes			

Version 2.0 – March 29, 2019

Amount of exudate	X	X	×	X	X
Wound shift (ratio necrotic/ fibrinous/ granulation/ epithelisation tissue)	×	×		X	X
Complete healing assessment		×	×	×	×
Wound photograph	×	×		×	×
Photograph of the investigational product on the wound***	×	×		X	×
Adverse events/Adverse device effects	×	×		×	×
Global dressing investigator evaluation		×		×	×
Global dressing subject's evaluation				X	×
Concomitant treatment	×	X		×	X

^{*} optional, if required by wound's condition

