7.2.2.2 Intermediate visit (V2, D3±2)

The intermediate visit must be planned three days after the first investigational product application. If appropriate, a window of two days before or after this expected visit is allowed to make sure that the patient will have the first dressing change as early as necessary according to their condition (i.e. already on the next day after V1).

Adverse events (AEs) / Serious adverse events (SAEs) / Adverse device effects (ADEs) and Device deficiencies (DDs) occurring since the previous visit will be collected by the investigator. Any changes to the concomitant therapy will also be collected. The investigator will also ensure that the subject continue the investigation.

The presence of complete healing status (100% of epithelialization, first epithelia layer) of the wound) will be assessed.

NB! In case of complete epithelialization all procedures, required for Visit 3 should be

performed, data is to be recorded in the CRF section Visit 3. Visit 2 should be marked as "Not performed due to early epithelialization" in the CRF.

Depending on the subject condition, analgesics may be concomitantly prescribed by the investigator. In this case, details on the type of prescribed treatments belonging to analgesic therapeutic class as well as hour of intake before removal (within 2 hours notably) will be recorded in the CRF.

A photograph of the wound with the investigational product in place will be taken before product removal (but after secondary dressing removal, if there was any), according to the photography guidelines (see Appendix 17.1).

The investigator will remove the investigational product by following the standardized removal procedure (see Appendix 17.2). Data about dressing soak will be collected in the CRF.

Pain at the first dressing removal will be assessed by using the visual analogue scale (VAS). The investigator will ask the subject to assess his/her pain level at the dressing removal. The subject will be asked to rate the pain he/she felt at the moment of dressing change using the VAS tool.

After product removal, a photograph of the wound will be taken according to the photography guidelines.

The investigator will assess the wound and surrounding skin condition:

- Wound size estimation
- Assessment of the wound bed (bleeding, maceration, inflammation, infection, ratio necrotic/ fibrinous/ granulation/ epithelisation tissue, and tissue in-growth in the dressing holes)

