The investigator will remove the investigational product by following the standardized removal procedure (see Appendix 17.2). Data about dressing soak will be collected in the CRF.

After product removal, a photograph of the wound will be taken according to the photography guidelines.

The investigator will assess the wound and surrounding skin condition:

- Wound size estimation
- Assessment of the wound bed (bleeding, maceration, inflammation, infection, ratio necrotic/ fibrinous/ granulation/epithelisation tissue, and tissue in-growth in the dressing holes)
- Assessment of the surrounding skin (inflammatory signs, irritation, allergic rash/eczema, blistering, skin stripping, maceration, dry, trauma to wound edges, product degradation on the skin, hematoma)
- Global assessment of exudate management (efficiency of the CL to drain exudates to the secondary dressing)

The presence of complete healing status (100% of epithelialization, first epithelia layer) of the wound) will be assessed.

The investigator will evaluate the use of the dressing regarding the following parameters:

- Ease of handling
- Ability to maintain its integrity
- Ease of application
- Ability to be repositioned during application
- Conformability
- Wound adhesion
- Ability of dressings to stay in place
- Transparency
- Ease / speed of removal,
- Overall impression,
- Absence of residue

The global assessment of the product by the patient will also be performed.

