7.8.2 Efficacy Measurements and Variables

7.8.2.1 Main Objective

Variable

The main criterion corresponds to the percentage of non-painful dressing removals defined as the percentage of dressing removals associated with a value < 30 mm on a VAS assessing pain scale (0 to 100 millimeters) evaluated at the first dressing removal (V2, D3±2).

This 30 mm threshold is recognized to differentiate a weak pain (score <30 mm) from a moderate (score ≥30 mm) to severe (score >50 mm) one [9-12].

Measurement

Subjects will be asked by investigators to rate their pain intensity perceived at the first dressing removal (V2, D3±2). Pain assessment will be performed using a Visual Analog Scale (VAS). The VAS is a 100 mm straight line ranging from 0 to 100, on which the subject will indicate his/her pain. Subjects will beforehand be informed that the beginning of the scale refers to "no pain" (0) and the end to the most severe intensity of pain they can have (100). Painless dressing change is defined as pain < 30 mm on the VAS. The results obtained during the first dressing removal visit (V2, D3±2) will be filled in by the investigator in the CRF.

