7.9.1.1 Population Analyses

Analyses will be performed on three populations as follows:

• The Safety population consists of all subjects allocated to treatment sample; and who had at least one investigational product applied.

- All randomized subjects with at least one exposure to either dressing will be included in the modified intent-to-treat (mITT) population. Subjects will be analysed in the treatment groups to which they will be randomly assigned (as per ITT principle).
- The per-protocol (PP) population consists of all enrolled subjects who satisfied the entry criteria of the investigation, who had an assessment of main criterion at V2 and who completed the treatment without major violations of the protocol.

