7.9.1.2 Efficacy analyses

Analysis of the main criterion

The test for the non-inferiority of Lomatuell Pro® vs UrgoTul® for the main criterion will be carried out through a confidence interval (CI) approach. Non-inferiority will be established if the lower unilateral limit of the 97.5% CI in the PP population for the between-treatment difference (Lomatuell Pro® - UrgoTul®) in the percentage of wound dressing associated with a pain < 30 mm on VAS at V2 does not exceed -10%.

Considering that the studied population is "patients with an acute wound" and that the primary endpoint will be assessed at V2 (Day 3±2); we can expect very few drop-outs. We also expect few patients with a major protocol deviation. Therefore, we can conclude that an assumption of 10% attrition rate is acceptable for this study.

In order to unambiguously conclude to non-inferiority in agreement with most of guidelines, the same analysis will be performed on the mITT population. In case of missing data to evaluate the primary criterion, the subjects will be considered as failures. The trial will be considered positive if both approaches support noninferiority.

Adjustment

The frequency of analgesic intake will also be analysed. In case of a significant difference between the 2 dressing groups, the analysis of the primary criterion (painless dressing removals) will be adjusted using a Mantel-Haenszel test.

Analysis of the secondary criteria

The following statistical tests will be used to analyse the secondary criteria according to the criteria type:

- Qualitative nominal criteria will be compared using a Chi² test.
- Qualitative ordinal criteria will be compared using a Mann-Whitney-Wilcoxon test
- Quantitative criteria will be compared using an analysis of variance (ANOVA)

Degree of significance

The criteria for which the degree of significance of the bilateral test will not exceed 0.05 (statistically significant difference) will highlight the specificities between the 2 groups of dressing.

Percentage of complete healing at V3

A wound will be considered as completely healed when there is 100% of epithelialization (first epithelia layer) of the wound. The percentage of wounds healed will be calculated based on a blind assessment from photographs using W.H.A.T.

Assessment of the wound condition

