10.2 Protocol Deviations

General definition: major protocol deviations are any protocol deviations that might significantly affect the completeness, accuracy, or reliability of the study data or that might significantly affect a subject's rights, safety, or well-being. Relevant major protocol deviations may include errors in treatment assignment, the use of excluded medication, poor compliance, loss to follow-up and missing data (cf. ICH E3. Questions and answers (R1). January 2013 and ICH E9).

In this trial, the following protocol deviations will be considered as major and will therefore lead to exclude patients from the PP set:

- Patient randomized while an inclusion criterion is not met
- Patient randomized while an exclusion criterion is met
- Patient not treated as per protocol between V1 (D0) and V2 (D3±2):
 - Patient randomized to Lomatuell Pro® but actually received UrgoTul® at D0
 - o Patient randomized to UrgoTul® but actually received Lomatuell Pro® at D0
- Pain assessment (VAS) during removal at V2 (D3±2) is missing (i.e. primary endpoint is missing)
- Pain assessment (VAS) during removal at V2 performed out of the time-window (i.e. at D6 or later)

Further major protocol deviations may be defined during the conduct of the trial, if deemed relevant. The list of major protocol deviations will have to be finalized and documented (for example, in the data review minutes) prior to the database lock.

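### A wound found healed at the first dressing change has Visit 2 marked as not performed, so its first-removal pain score may go unrecorded or be treated as missing: a failure in mITT, excluded from PP

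*Protocol*

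**What the plan says.** The main objective (Protocol 6.1) concerns "pain induced at first dressing removal in the management of acute wounds". The variable in 7.8.2.1 is a VAS below 30 mm, "evaluated at the first dressing removal (V2, D3±2").

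Section 7.2.2.2 foresees that the wound may already be fully epithelialised at this visit. The Visit 3 procedures are then done, the data go in the Visit 3 part of the CRF, and "Visit 2 should be marked as 'Not performed due to early epithelialization' in the CRF".

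In Table 1 (7.2.1) the row "Pain assessment (VAS) during removal" carries a single mark, which reads as V2. The Visit 3 list in 7.2.2.3 has no VAS item. It does repeat the instruction "The investigator will remove the investigational product by following the standardized removal procedure", and that procedure (Appendix 18.2, cited in the text as 17.2) contains a VAS step.

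The analysis rules refer to V2:
- PP (7.9.1.1) is restricted to subjects "who had an assessment of main criterion at V2".
- Section 10.2 lists as a major deviation "Pain assessment (VAS) during removal at V2 (D3±2) is missing (i.e. primary endpoint is missing"). Its time-window deviation covers only assessments at D6 or later.
- For mITT, section 7.9.1.2 states: "In case of missing data to evaluate the primary criterion, the subjects will be considered as failures". It makes no exception for early healing. The trial is positive only if PP and mITT both support non-inferiority.

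**The concern.** A patient whose wound has closed by the first dressing change still has a first removal inside the D1-D5 window, and that removal can be scored. The protocol foresees the case and gives it a CRF route, but does not say how it enters the primary endpoint. The score can be lost in two ways: it is not recorded because the Visit 3 pages do not ask for it, or it is recorded under Visit 3 and then treated as a missing V2 value.

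In either event the mITT rule turns a good outcome, early healing, into a pain failure, and PP drops the patient. If one dressing heals faster, mITT is biased against it. With a planned success rate of 95% (about 4 failures among 84), a few extra failures in one arm are not negligible.

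**Working it through.** **Inputs from the plan** (Protocol 7.9.1.2, 7.9.2): 95% painless in both arms, margin 10 points, one-sided alpha 2.5%, power 80%, 10% attrition, success required in both PP and mITT.

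**The plan's own figure.** n = (1.960 + 0.842)² × 2 × 0.95 × 0.05 / 0.10² = 74.6, so 75 per group; 75 / 0.90 = 83.3, so 84. Both reproduce. The sample size arithmetic is not at fault.

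**Assumptions.** The documents give no rate of healing at the first change, so all early-healing counts and rates below are assumed. Section 7.9.1.2 names no interval method. I use the Wald interval, which matches the sample size formula, and give Newcombe where the conclusion differs.

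**1. Fixed counts.** There are 84 per arm, 80 of 84 painless in each arm if every score counts, and no other missing data. With p_T and p_C the test and comparator proportions, the lower limit is (p_T − p_C) − 1.96 × √[p_T(1−p_T)/n_T + p_C(1−p_C)/n_C]. Each early healer scored as a failure removes one success.

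| Early healers as failures, test v comparator | mITT counts | Wald lower limit | Non-inferior? |
|---|---|---|---|
| 0 v 0 | 80 v 80 | -6.4% | yes |
| 2 v 0 | 78 v 80 | -9.5% | yes |
| 3 v 1 | 77 v 79 | -10.2% | no |
| 3 v 0 | 77 v 80 | -11.0% | no |
| 3 v 3 | 77 v 77 | -8.4% | yes |
| 0 v 3 | 80 v 77 | -3.9% | yes |

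For 3 v 0: difference -3.57 points, standard error 3.81 points, and -3.57 − 1.96 × 3.81 = -11.0 points.

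In PP these patients are removed rather than failed. At 3 v 0, PP is 77/81 v 80/84, with lower limit -6.7%. At 0 v 3 it is 80/84 v 77/81, with -6.4%. So at 3 v 0 mITT fails while PP passes.

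With Newcombe, 2 v 0 already fails (-10.5%). With Wald, 2 v 0 also fails if two other patients per arm are missing: 76 v 78 gives -10.7%.

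**2. Chance of a test-arm excess of three or more**, from two independent Binomial(84, h) counts, h being the early-healing rate:
- 1% in both arms: 2.7%
- 2% in both arms: 7.9%
- 3% test v 1% comparator: 31%

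**3. mITT power with the planned attrition.** Success rate 0.95 × (1 − h) × 0.90 in both arms, 84 per arm, exact enumeration of the Wald rule.

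| h | Success rate | mITT power |
|---|---|---|
| 0% | 85.5% | 46% |
| 1% | 84.6% | 45% |
| 2% | 83.8% | 43% |
| 5% | 81.2% | 39% |

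Unrounded, power goes from 46.5% to 44.7%, 43.1% and 38.9%, an added loss of about 2, 3 and 8 points. The 46% starting level comes from scoring attrition as failure and is a separate matter. Without attrition the same method gives 83.7%, 78.0%, 72.8% and 60.2%.

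**4. Direction.** If the comparator heals faster, mITT is flattered (0 v 3 gives -3.9%). PP must still pass, and it does not score these patients as failures, so this is not a route to a false positive.

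**The case against.** The strongest reply is that the protocol already implies the right answer. Full epithelialisation is normally confirmed with the dressing off, and Appendix 18.3.2 asks for the VAS immediately after removal and for the result to be noted on the CRF. The standardised removal procedure, which also applies at Visit 3, contains the same step. The objective and the variable are defined by the first removal, a recorded score is not missing, only D6 or later is out of window, and 10.2 lets the deviation list be finalised before database lock. Cases should also be rare: 7.3.1 and 7.3.2 require wounds of 3 to 24 cm² with loss of dermis. At 0.5% in both arms, the chance of a test-arm excess of three or more is 0.6%.

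Much of this stands, and it is why the point is that the score may be lost, not that it will be. It does not close the gap. Nothing says that a score filed under Visit 3 is the primary criterion, while 7.9.1.1 and 10.2 both say V2. Finalising the deviation list neither changes the mITT rule nor recovers a score never taken. The CRF was not available to show whether Visit 3 has a field for it. The supplied SAP (section 4) is written for the Suprasorb C protocol and has no rule for this endpoint.

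A second reply is that the fixed-count example assumes no other missing data. That is correct. With the planned 10% attrition scored as failure, about 72 v 72, the Wald limit is -10.6% and mITT fails with no early healers at all. The example shows sensitivity when attrition is low; the power figures show the added loss when it is as planned.

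**Conclusion.** The concern holds. The protocol foresees healing at the first dressing change, marks the visit that carries the primary endpoint as not performed, and does not say whether the pain score from that removal counts. Under a literal reading it is missing: failure in mITT, excluded from PP.

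The size depends on an early-healing rate that the documents do not give and that is probably low. An imbalance of two or three patients could make mITT fail while PP passes, depending on the interval method and on other missing data. At assumed rates of 1% to 5% in both arms, with planned attrition, the cost is about 2 to 8 points of mITT power.

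This should be fixed, with medium confidence. It threatens the trial's ability to show true non-inferiority, not the validity of a positive result.

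**What to change.** - In Table 1 and 7.2.2.2, require the VAS at the first removal of the study dressing within D1-D5, including when the visit is filed as Visit 3. Add a field to the Visit 3 CRF page if it has none.
- In 7.8.2.1, 7.9.1.1, 7.9.1.2 and 10.2, state that this score is the primary criterion for both mITT and PP, whatever visit label the CRF carries.

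The cost is at most one CRF field and a short amendment. The removal procedure already includes the VAS, so no extra patient contact is needed. The change should be made early, because a score that was not taken cannot be recovered at data review.

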7.2.2.4 Additional visits

Between V2 and V3, additional dressing changes can be performed as often as necessary according to the instruction for use of the investigational product assigned. Lomatuell Pro® and UrgoTul® may be left in place up to 7 days. In this case, the data collected during these "in-between" visits will be collected in the Nurse Diary.

Data collected during these visits are:

- Number of the additional visit
- Date of the visit
- Reason for dressing change

- Presence of complete re-epithelialization (NB! In case of complete epithelialization all procedures, required for Visit 3 should be performed, data is to be recorded in the CRF section Visit 3 and not as an additional visit)
- Appearance of the dressing before removal
- Bleeding during dressing removal
- Appearance of the wound bed (bleeding, maceration, inflammation, infection, and tissue in-growth in the dressing holes)
- Appearance of the surrounding skin (inflammatory signs, irritation, allergic rash/eczema, blistering, skin stripping, maceration, dry, trauma to wound edges, product degradation on the skin, hematoma)
- Amount of exudate
- Wound moisture
- Local treatment
- Number of dressings used
- Application of dressing
- Secondary dressing
- Initials of person in charge for dressing change

7.2.2.5 Early termination visit

This visit will be registered for the patients who discontinued the study preliminary for any reason, including consent withdrawal, loss to FU or death, instead of the visit V3, and the list of the procedures should be if, to the extent possible, the same as for V3.

In case of consent withdrawal / lost to FU date of the patient's / nurse's decision to discontinue study participation should be entered in the CRF as the date of "early termination" visit with all other fields marked as NA. In case of patient's death date of the death should be entered as the date of this visit with all other fields marked as NA.

For the patient, who voluntary discontinued the treatment, Adverse events (AEs) / Serious adverse events (SAEs) / Adverse device effects (ADEs) and Device deficiencies (DDs) occurring since the previous visit should also be collected by the investigator, if patient agrees to provide this information. Any changes to the concomitant therapy should also be collected.

If the reason of the early termination is not: withdrawal of consent, patient lost to follow-up or death (cf §7.3.3); then the following data should be collected as possible:

 Depending on the subject condition, analgesics may be concomitantly prescribed by the investigator. In this case, details on the type of prescribed treatments belonging to analgesic therapeutic class as well as hour of intake before removal (within 2 hours notably) will be recorded in the CRF.

- A photograph of the wound with the investigational product in place will be taken before the investigational product removal (but after secondary dressing removal, if there was any), according to the photography guidelines (see Appendix 17.1).
- The investigator will remove the investigational product by following the standardized removal procedure (see Appendix 17.2). Data about dressing soak will be collected in the CRF.
- After product removal, a photograph of the wound will be taken according to the photography guidelines.
- The investigator will assess the wound and surrounding skin condition:
 - Wound size estimation
 - Assessment of the wound bed (bleeding, maceration, inflammation, infection, ratio necrotic/ fibrinous/ granulation/epithelisation tissue, and tissue ingrowth in the dressing holes)
 - Assessment of the surrounding skin (inflammatory signs, irritation, allergic rash/eczema, blistering, skin stripping, maceration, dry, trauma to wound edges, product degradation on the skin, hematoma)
 - Global assessment of exudate management (efficiency of the CL to drain exudates to the secondary dressing)
- The presence of complete healing status (100% of epithelialization, first epithelia layer) of the wound) will be assessed.
- The investigator will evaluate the use of the dressing regarding the following parameters:
 - Ease of handling
 - Ability to maintain its integrity
 - Ease of application
 - Ability to be repositioned during application
 - Conformability
 - Wound adhesion
 - Ability of dressings to stay in place
 - Transparency
 - o Ease / speed of removal,
 - Overall impression,
 - o Absence of residue
- The global assessment of the product by the patient will also be performed.

